Potential mechanisms by which EEN might act include relative bowel rest, reduced antigenic load, provision of trophic amino acids, local anti-inflammatory effects, and modification of gut microbiota^{11,20}. However, there is no strong evidence to fully support any one of these mechanisms. A recent meta-analysis²⁰ showed that the effects of the therapeutic formula on specific bacterial strains were variable and inconsistent among studies, possibly due to small sample sizes and methodological limitations. Our preliminary data showed that short term dietary changes improve motility in patients with low-grade gut inflammation²¹. However, the effects of EEN on gastrointestinal transit in adults has not been yet investigated.

Evidence for the effect of EEN on quality of life, an essential patient reported outcome, is particularly scarce. Guo *et al*³⁰ found an improvement of quality of life in 13 patients with CD receiving EEN for 6 weeks. However, it is currently unknown whether EEN is more effective than CS in improving quality of life in adults with CD.

The potentially synergistic effects of adding EEN to CS therapy have not been explored before. Therefore, we designed a randomized controlled trial with the objective to investigate the effect of EEN in addition to different regimes of CS therapy (ECS) compared to CS alone (CS), for decreasing disease activity and improving quality of life in adult patients with CD. We also propose to investigate potential mechanisms underlying any beneficial effect of EEN in CD in the context of concomitant CS therapy.

Hypotheses:

- 1- Six weeks of ECS will be more effective than CS in inducing clinical remission in patients with active CD
- 2- Six weeks of EEN in addition to a short course of CS (ECSC) will have similar efficacy than ECS and reduced number of adverse events
- 3- Six weeks of ECS will lead to beneficial changes in the composition and/or metabolic activity of the intestinal microbiota, gastrointestinal transit and inflammatory burden.

Because the effect size of ECS has not been investigated before, we will perform a pilot study to assess feasibility and calculate estimates of effect size in order to plan a larger trial. Based on the significant number of patients, if the study is feasible, we will consider the sample size estimated through this pilot study for the full trial to minimize the possibility of recruiting additional patients.

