General aim and endpoint: To assess study feasibility and provide estimated effect sizes (point estimates with confidence intervals) for all measures of interest in order to plan an adequately powered study. We will assess recruitment rates and acceptability of treatment in arms involving exclusive enteral nutrition.

Primary outcome and endpoint: To assess the efficacy of 6 weeks of ECS in inducing remission (CDAI <150) compared to treatment with CS in adult patients with active CD (CDAI >220 and either CRP >5 or fecal calprotectin >250 mg/l).

Secondary outcomes and endpoints: To determine the beneficial effect of 6 weeks of ECS as compared to CS in inducing:

1. Clinical disease improvement (drop in CDAI >70 or 100)
2. Improvement in quality of life (using the Inflammatory Bowel Disease Questionnaire (increase IBDQ scores))
3. Biochemical remission (normalization of either serum CRP and/or fecal calprotectin)
4. Changes in microbiota composition (16S sequencing Illumina)
5. Normalization of colonic transit (SHAPE 0-5 markers at day 5)³⁴ among those with altered transit at baseline
6. Decrease in anxiety and/or depression scores (decrease >2 points HAD-A and/or HAD-D scores)
7. Increase in body weight and improvement in nutritional status (increased levels of micronutrients)
8. Decrease of indirect markers of mucosal integrity (IFABP2)
9. Changes in bacterial fermentation profile (SCFAs: acetate (acetic acid), propionate (propionic acid), and butyrate (butyric acid))^{26,27}.
10. Decreased number of adverse events

METHODS

Study design

Protocol date: October 2018

Randomized control trial; 3 arms of treatment: EEN plus standard or short course of CS (ECS, ECSC) vs CS alone (CS) conducted at McMaster University Medical Centre (Figure 1). The study will last 10 weeks and will involve 4 visits. At the screening visit, we will assess clinical history and symptoms, perform a physical exam and complete bloodwork after the informed consent is signed. Randomization will occur at the second visit (pre-treatment), when the inclusion and exclusion criteria and symptoms will be re-assessed, and baseline stool and urine samples will be collected. In addition, we will perform a SHAPE study and patients will be assessed by a dietitian or clinical nutrition support specialist to assess dietary factors and estimate energy needs using the Harris Benedict equation as detailed below.

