2. Confirmed CD diagnosis for at least 6 months
3. Clinically active disease (CDAI >220 or HBI>6) or evidence of activity in endoscopy
4. Biochemical evidence of disease activity (CRP > 5 and/or fecal calprotectin > 250),

Exclusion criteria:

1. Current treatment with EEN
2. Intestinal obstruction, perforation, toxic megacolon, massive gastrointestinal bleeding, abdominal abscess, or other criteria considered by the investigator which preclude the use of EEN;
3. Stricture disease
4. Previous intestinal resection with a remnant bowel <180 cm
5. Treatment with prednisone in last 30 days;
6. New start or change in dose of azathioprine, 6-mercaptopurine, cyclosporine, other immunosuppressant or biologics in the last 90 days. Doses of these medications must also remain unchanged for the duration of the study.
7. New start or change in dose of 5ASA in last 30 days. 5ASA dose must remain unchanged for the duration of the study.
8. Treatment with antibiotics or probiotics use in the last 30 days.
9. Pregnancy or lactation
10. Any serious illness considered by the investigator that will interfere with the study procedure or results.

Intervention

Participants will be randomized to one of the following interventions:

1. Exclusive enteral nutrition plus corticosteroids

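### The primary endpoint is stated for patients with CDAI above 220, but entry is also allowed by HBI or endoscopy with no CDAI minimum, and the analysis set is not named

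*Combined protocol and SAP*

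**What the plan says.** The paragraph headed Primary outcome and endpoint sets the aim as "inducing remission (CDAI <150") with ECS compared with CS, and states the population in the same sentence: "in adult patients with active CD (CDAI >220 and either CRP >5 or fecal calprotectin >250 mg/l"). Hypothesis 1 has the same focus: "Six weeks of ECS will be more effective than CS in inducing clinical remission in patients with active CD".

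Inclusion criterion 3 reads "Clinically active disease (CDAI >220 or HBI>6) or evidence of activity in endoscopy". The three routes are alternatives, and only the first involves a CDAI value. Criterion 4 must also be met, "Biochemical evidence of disease activity (CRP > 5 and/or fecal calprotectin > 250"), but it sets no CDAI level.

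Three other places could have closed the gap and do not:

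- Subject recruitment enrols anyone who meets all inclusion criteria and no exclusion criterion, and no exclusion criterion mentions CDAI.
- Study design has the same criteria re-assessed at visit 2, with no CDAI minimum added.
- Statistical analysis assigns intention to treat to the primary outcome and names no subset by baseline CDAI.

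CDAI is listed under Measurements before and after treatment, so a baseline value is planned. The visit at which it is taken is not stated.

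**The concern.** Remission is an absolute threshold, with no fall from baseline required. It measures induction only in patients who start above the threshold. The endpoint sentence secures that by requiring CDAI above 220; criterion 3 does not. For a patient who starts below 150, the same endpoint measures staying in remission.

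The general aim is to supply effect estimates for planning a powered trial, and the text after the Hypotheses adds that "we will consider the sample size estimated through this pilot study for the full trial to minimize the possibility of recruiting additional patients". An estimate used that way needs a defined population. Treatment is also open-label, so a primary set left unnamed could be settled after results are visible.

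**Working it through.** **The plan's own figure.** 100 recruited × 0.90 retained ÷ 3 arms = 30 per arm, as stated under Participants. This reproduces.

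**Logic check.** Take a patient with endoscopic activity, calprotectin above 250 and CDAI 110. Criteria 3 and 4 are met, and the patient can be randomised if the other criteria are also met. If CDAI at week 6 is still 110, the result depends on the analysis set:

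- All randomised patients: counted as a remission, with no change.
- Only CDAI above 220 at baseline: not in the primary comparison, which then has fewer than 30 per arm.

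No section says which applies.

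**Illustration of size.** The documents give no remission rate for ECS or CS; Background gives only up to 60% for EEN. They also do not say how many patients would enter by each route. Every rate and share below is therefore an assumption.

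Let f be the share entering below 150. Assume remission of 60% (CS) and 80% (ECS) in everyone else, including those entering at 150–220. Let r be the share of low entrants still below 150 at week 6.

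Observed rate in an arm = (1 − f) × p + f × r.

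With r = 90% in both arms, meaning no treatment effect among low entrants:

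| f | CS | ECS | Difference |
|---|---|---|---|
| 0 | 60% | 80% | 20 points |
| 10% | 0.9×60 + 0.1×90 = 63% | 0.9×80 + 0.1×90 = 81% | 18 points |
| 20% | 0.8×60 + 0.2×90 = 66% | 0.8×80 + 0.2×90 = 82% | 16 points |
| 30% | 0.7×60 + 0.3×90 = 69% | 0.7×80 + 0.3×90 = 83% | 14 points |

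Equal retention drives this result. With r = 80% on CS and 90% on ECS, f = 30% gives CS 0.7×60 + 0.3×80 = 66%, ECS 83%, and a difference of 17 points.

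**Comparison with the pilot's precision.** Half-width = 1.96 × √[(p₁q₁ + p₂q₂)/n]. At 60% against 80%, p₁q₁ + p₂q₂ = 0.24 + 0.16 = 0.40.

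- n = 30: 1.96 × √(0.40/30) = 22.6 points.
- n = 21 (30% at or below 220 left out): 27.1 points.
- n = 15 (50% left out): 32.0 points.

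The loss of 2–6 points in the table is small against 22.6.

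**Does restriction gain precision?** At f = 30% and r = 90%, analysing everyone gives 14 ± 21.3 points, a difference-to-half-width ratio of 0.66. Restricting to CDAI above 220 gives 20/27.1 = 0.74 if nobody enters at 150–220, but 20/32.0 = 0.62 if a further 20% do. It can go either way.

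**The case against.** The strongest reply is that there is no mis-scoring at all. The endpoint sentence itself carries CDAI above 220, so taken literally a patient entering at 110 lies outside it; criterion 3 may simply govern enrolment. Intention to treat does not by itself override that. This stands to the extent that a reader might infer that the plan definitely counts unchanged patients as induced remissions, and the documents do not support that. They show two populations and no rule for choosing between them. The reply does not remove the problem, because on its reading the stated 30 per arm overstates the primary set whenever anyone enters at or below 220.

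Broad entry is also defensible in a single-centre pilot where recruitment rate is a feasibility aim. That stands too, and it is why one of the two fixes keeps it.

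Other stronger readings a reader might infer do not hold:

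- **Bias towards an arm.** Low entrants are randomised like everyone else. Entry route is not a stratum, so balance holds only on average, but nothing points systematically to one arm.
- **The same fault by the HBI route.** The documents give no mapping between HBI and CDAI, so they do not show that a patient with HBI above 6 could start below 150.
- **A wrongly sized full trial.** If that trial keeps the same entry rule, the diluted difference is right for its population. Sizing is misled only if it recruits the CDAI-above-220 population.
- **Broken CDAI endpoints.** Secondary item 1 is "Clinical disease improvement (drop in CDAI >70 or 100"). From above 220, reaching below 150 needs a fall of more than 220 − 150 = 70, so remission implies the 70-point response, and broad entry breaks that link (160 to 145 is a fall of 15). For the 100-point version the link already fails inside the narrower population: 225 to 145 is a fall of 80. No section requires remission to imply response.

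**Conclusion.** The primary endpoint's population and criterion 3 disagree, and no other section reconciles them. Under an analysis of all randomised patients, the endpoint does not measure induction in anyone who enters below CDAI 150; under the narrower reading, the primary set is smaller than stated.

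The numerical effect is unknown and may be near zero: no study endoscopy is scheduled, criterion 4 must also be met, and nothing indicates how many patients below 150 would enter. The illustrated loss of 2–6 points rests on assumed rates, an assumed 10–30% share and equal retention in both arms; the milder retention assumption halves the loss at a 30% share to 3 points. All of this lies within the pilot's own uncertainty. The contradiction itself rests on none of these assumptions. Severity is minor.

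**What to change.** Reconcile the endpoint sentence with criterion 3 in one of two ways.

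**(a)** Align criterion 3 with the population in the primary endpoint. This changes one line. The cost is a smaller recruitment pool at a single centre.

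**(b)** Keep broad entry and add to Statistical analysis:

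> CDAI is recorded for every patient at or before visit 2, before randomisation. CDAI remission and CDAI response are analysed by intention to treat among all randomised patients whose last pre-randomisation CDAI was >220; the same analysis in all randomised patients is also reported. All randomised patients, whatever their baseline CDAI, remain in all other secondary outcomes and in the adverse-event comparison.

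Option (b) selects on a value taken before randomisation, so the comparison stays randomised. It needs no new measurement, only a stated time for the CDAI. The plan already limits one endpoint by baseline status: colonic transit is assessed "among those with altered transit at baseline". The cost is a smaller primary set, because everyone at or below 220 leaves it and not only those below 150. At 60% against 80% the half-width becomes about ±27 points at 21 per arm and ±32 points at 15 per arm.

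The gain from either option is that the estimate matches the stated objective. No gain in precision is claimed.

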Patients will be instructed to take the allocated treatment and to collect empty bottles/blisters of medication to assess the compliance at the next visit. Six weeks later (visit 3), their symptoms will be re-assessed, blood, urine and stool samples collected and SHAPE study performed. Patients will be instructed to stop the EEN or decrease the dose of CS, as detailed in the section “Follow up after treatment”. In the last visit (4th visit; 10 weeks after enrollment) we will collect information on symptoms, stool samples and urine.

The study protocol will be submitted by the investigator for approval by the Hamilton Integrated Research Ethics Board (HiREB).

Randomization process

The sequence of the treatments will be randomly generated using a computer-based pseudo-random number generator (RStudio Team (2015). RStudio: Integrated Development for R. RStudio, Inc., Boston, MA) Patients will receive one of challenges A,

B, or C consisting of CS, ECS or ECSC. A third person not involved in the study will perform the randomization to preserve treatment allocation concealed from participants and study staff. A block randomization will stratify patients by disease location (colonic/small bowel involvement). Each treatment will be assigned a number according to the randomization sequence. On recruitment, the patient will be assigned into one of three strata and given the next consecutive randomization number available for that stratum. Treatment will be not blinded for patients or study staff.

Subject recruitment

Subjects will be recruited from McMaster University Medical Centre (MUMC) Digestive Diseases Clinic, identified in an ongoing database organized in 2008 and by recruitment flyers posted at McMaster University Medical Centre, Juravinski Hospital and Hamilton General Hospital. Patients in the database signed an informed consent agreeing to be contacted for future research. Patients will be contacted by study personnel and invited to participate in the study.

After the subject has provided written consent to participate, an inclusion checklist will be completed. Subjects will be enrolled after having fulfilled all inclusion criteria, and none of the exclusion criteria.

Participants

One hundred adult patients diagnosed with IBD will be recruited at McMaster University Medical Centre. This will provide 30 subjects in each treatment arm, allowing for 10% dropout rate.

Inclusion criteria:

1. Adult patients (age 18-75 years)

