Patients randomized to ECS or ECSC arms will receive EEN defined as enteral feeds given exclusively as sole nutritional source over 6 weeks period in addition to the CS therapy. Hypercaloric polymeric formula (Modulen 1.5 kcal /ml; Nestle ^{22,23}) will be used for a period of 6 weeks. To increase palatability, patients will be allowed to add the “Nestle Nutrition Flavour Mix” (see Appendix). Daily volumes of formula will be prescribed based upon the patient’s estimated energy requirement (EER), calculated using the Harris Benedict equation (calculator available at <https://manytools.org/handy/bmr-calculator>), which estimates basal metabolic rate from weight and height and then applies an activity factor which ranges from 1.2 to 2.4 (Sedentary AF 1.2; mild activity 1.375, moderate activity AF 1.55, heavy activity AF 1.7, extreme AF 1.9 For details, refer to Appendix). Actual body weight or ideal body weight for height will be used in the equation depending on whether the patient is of an appropriate weight or underweight for height. Oral administration will be encouraged wherever possible, with formula volume distributed as set meals and snacks throughout the day. Nasogastric (NG) tube insertion for delivery of formula will be discussed and offered only if oral supplementation is not possible or not tolerated by the patient. Enteral feeding will be prescribed as an exclusive therapy, with exclusion of all normal diet for the period of feeding. Patients will be reviewed after 3 weeks of therapy and, when required, energy intakes will be modified by adjusting formula volumes based upon adequacy of weight changes. Volume taken per meal and distribution during the day will be recorded in the case report form. No oral foods or fluids

(except for clear liquids including water and weak tea or coffee) will be allowed during the study period. Vitamins and supplements will be allowed if doses have been stable before entering in the study, and doses are not changed during the study.

2. Corticosteroids

Patients in ECS and CS arms will receive oral prednisone 40 mg x day for 2 weeks; with subsequent taper of daily dose by 5 mg per week. Patients randomized to ECSC arm will receive oral prednisone 40 mg x day for 3 days and taper in 16 days (Figure 1). Patients randomized to the CS arm will be asked to maintain their regular diet.

Follow up after treatment

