- Systemic priming to gut bacteria ([name] Lab using Flow cytometry after incubating patients' serum with cultured fecal bacteria¹⁶)
- First urine morning for metabolomics
- Intestinal permeability – indirect markers of mucosal integrity (FABP2)

Statistical analysis

There is no previous estimate on the effect of ECS compared to CS in inducing symptomatic improvement and associated changes in gut microbiota composition. Therefore, a sample size of 30 patients per arm^{28,29} should be sufficient to estimate the results and allow us to plan for future larger study. We will recruit additional 10 patients in total, to account for drop outs rates. Results will be analyzed as intention to treat (for primary outcome) and per protocol (excluding patients non-compliant with EN). The results will be expressed as n (%), mean (SD) or median (IQR) as appropriate. We will perform logistic regression to assess the association between symptomatic response and significant changes in gut microbiota composition in each group. T test or Man Whitney U test will be used as appropriate to assess differences between means. Analysis will be performed using SPSS version 21 (San Diego, CA).

Early withdrawals:

The following criteria will be considered as reasons for early discontinuation from the study (drop outs):

- Patient's decision.

- Physician's decision in case that the continuation of the patient in the study places him/her at risk.
- Patients that were not compliant with the unauthorized concomitant diets/treatments/medication will be considered as non-compliant and considered for the ITT analysis. If a subject's outcome measures worsen to the degree that they meet the study's Exclusion Criteria, study treatment will be withdrawn. Medical care will be provided as directed by the study physician and/or the subject's physician. If the required medical care conflicts with the study protocol, the subject will be placed in the intent-to-treat group. Study safety follow up will continue unless the subject withdraws, and/or is withdrawn by the study physician, and/or on the advice of the subject's physician.

Handling of adverse events

Reporting and documentation of adverse events

All adverse events occurring during the study will be reported and recorded whether or not they are considered to be non-serious, serious and/or related to the treatment. The following information will be required in each case:

- Subject and date
- Description of event
- Duration
- Frequency

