***Standard corticosteroids tapering regimen (ECS)**

Week	1	2	3	4	5	6	7	8	9	10
CS mg/day	40	40	35	30	25	20	15	10	5	5 mg every other day

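### The only contact between treatment start and week 6 is written for the two EEN arms, so adverse events may be detected unequally in the ECS versus CS comparison

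*Combined protocol and SAP*

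**What the plan says.** - **Week-3 review.** Item 1 of the Intervention section opens with "Patients randomized to ECS or ECSC arms will receive EEN defined as enteral feeds given exclusively as sole nutritional source". The same paragraph contains the only mention of a mid-treatment review: "Patients will be reviewed after 3 weeks of therapy and, when required, energy intakes will be modified by adjusting formula volumes". The adjustment depends on weight change. Adverse events are not mentioned there.
- **Visit plan.** Under Study design, "The study will last 10 weeks and will involve 4 visits": screening, pre-treatment (with randomization), week 6 and week 10. After the pre-treatment visit the next entry is "Six weeks later (visit 3), their symptoms will be re-assessed, blood, urine and stool samples collected and SHAPE study performed". Item 2 of the Intervention section, on corticosteroids, adds no contact for the CS arm.
- **Endpoint.** Item 10 of the secondary outcomes, which compare ECS with CS, is "Decreased number of adverse events".
- **Recording rule.** "All adverse events occurring during the study will be reported and recorded", in every arm. The section lists what to document for each event, but not when or how patients are asked.
- **Context.** The Randomization process section makes the trial open-label. Appendix 2, a 22-item steroid checklist, is labelled for visit 2, which is the pre-treatment visit. A paper diary is given at visit 1 to help assess compliance.

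**The concern.** As written, ECS and ECSC patients have three scheduled contacts after treatment starts (weeks 3, 6 and 10) and CS patients have two (weeks 6 and 10). With no set schedule of enquiry, what is recorded depends on when patients and staff meet. A patient seen at week 3 can mention a recent event, whereas a CS patient must recall the same event at week 6.

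A nutritional review also touches the protocol's own adverse-event items. It looks at weight, and weight gain is on the Appendix 2 list. Formula tolerance is a natural topic, and it overlaps with bloating, nausea or vomiting, and diarrhea on that list.

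At stake is the adverse-event estimate for ECS versus CS. The pilot is meant to supply effect estimates for all measures of interest, and the Hypotheses section contemplates using the pilot towards the full trial, so a distorted count would carry forward. Separately, CS patients take most of a standard prednisone course before anyone is scheduled to speak to them.

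**Working it through.** **1. Prednisone taken before the first scheduled contact.** The documents state no cumulative dose, so there is no figure of their own to reproduce. The inputs are the corticosteroid paragraph (the CS and ECS arms share one regimen) and the standard taper table under Figure 1: 40, 40, 35, 30, 25, 20, 15, 10 and 5 mg/day in weeks 1–9, then 5 mg every other day in week 10.

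- To end of week 6: 7 × (40+40+35+30+25+20) = 7 × 190 = 1330 mg.
- Weeks 1–9: 7 × 220 = 1540 mg. Week 10 adds 3 or 4 doses of 5 mg, giving 1555–1560 mg.
- CS, first contact at week 6: 1330/1560 = 85.3% to 1330/1555 = 85.5%. Using the text taper alone, without the week-10 step, 1330/1540 = 86.4%.
- ECS, first contact at week 3: 7 × (40+40+35) = 805 mg, about 52%.
- ECSC: 3 × (40+30+20+10+5) = 315 mg by day 15, or 320–330 mg with one to three alternate-day doses (number assumed). On that reading the whole course precedes the week-3 review.

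**2. Possible size of unequal detection.** The documents give no recall or detection rates, so everything in this step is assumed. Let true event rates be equal in the arms and events be spread evenly over time. An event is reported with probability 0.9 if asked about within 3 weeks, and with probability r = 0.6 (range 0.4–0.8) if asked about later. Suppose also that the week-3 review works as a full enquiry.

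Weeks 1–6:

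- CS capture = 0.5r + 0.5 × 0.9.
- EEN capture = 0.5 × [1 − 0.1 × (1 − r)] + 0.5 × 0.9, because an event missed at week 3 may still be recalled at week 6.

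Weeks 7–10, where every arm has the same contact at visit 4 (taken as week 10 of treatment): capture = 0.75 × 0.9 + 0.25r. The 10-week ratio weights the two periods 0.6 and 0.4.

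| r | CS, wk 1–6 | EEN, wk 1–6 | Ratio, wk 1–6 | Capture, wk 7–10 | Ratio, 10 wk |
|---|---|---|---|---|---|
| 0.4 | 0.65 | 0.92 | 1.42 | 0.775 | 0.862/0.700 = 1.23 |
| 0.6 | 0.75 | 0.93 | 1.24 | 0.825 | 0.888/0.780 = 1.14 |
| 0.8 | 0.85 | 0.94 | 1.11 | 0.875 | 0.914/0.860 = 1.06 |

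If the review prompts no reports at all, both ratios are 1.00.

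**3. Would counting only events elicited at visits 3 and 4 repair it?** Take r = 0.6 and suppose EEN patients do not repeat at visit 3 what they reported at week 3. EEN capture over weeks 1–6 is then 0.5 × 0.1 × 0.6 + 0.5 × 0.9 = 0.48, against 0.75 in CS. The ratio is 0.48/0.75 = 0.64, so the bias would turn towards the hoped-for decrease.

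**The case against.** A reader might infer that adverse events are actively sought more often in the EEN arms and that outcome 10 is therefore biased. The documents do not show this. The review's only stated purpose is to adjust intake, and no arm has a schedule of adverse-event enquiry. Unequal detection is a likely consequence of unequal contact, not a documented procedure, and an excess of zero is possible.

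A reader might also take the 85% figure as evidence of bias, or as a gap peculiar to CS. It is neither. It describes timing only, and by the week-3 review ECSC has taken essentially all its prednisone and ECS about half. Nor are CS patients necessarily unseen. They have no scheduled contact, but unscheduled reports are not excluded, and the Early withdrawals section provides for medical care and continued safety follow-up. The graphic in Figure 1 was not available in the text reviewed, so a CS contact drawn there cannot be ruled out.

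The consequence is limited too. This is one of ten secondary outcomes in a pilot, and the bias probably works against the sponsor's hypothesis. The adverse-event part of Hypothesis 2 compares ECSC with ECS, which both have the review.

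These limits stand. They leave intact the written difference in contact, the requirement to record every event, and the absence of any common enquiry to offset the difference.

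**Conclusion.** The point holds as a risk of unequal detection that should be removed, not as a demonstrated bias. The written schedule gives three post-start contacts in ECS and ECSC and two in CS. In an open-label trial with no set enquiry, that may inflate ECS relative to CS on outcome 10 and so mask a true reduction.

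The size cannot be computed from the documents. The illustrative excess of about 24% over weeks 1–6, or about 14% over 10 weeks, rests on assumed recall, evenly spread events and a review that works as a full enquiry. The lower bound is 0%.

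What the documents do establish is that CS patients have no scheduled contact in the available text until 1330 of 1555–1560 mg of prednisone, about 85%, has been taken. They also show that the only adverse-event checklist carries a pre-treatment visit label. It could serve as a baseline there, but no on-treatment use is scheduled for any arm.

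**What to change.** - Schedule a week-3 contact in all three arms; for CS a short telephone call is enough. Ask the same open adverse-event question and the Appendix 2 items in each arm, and repeat the same enquiry at visits 3 and 4.
- Add an adverse-event line to the diary already given at visit 1.
- Reconcile the visit 2 label on Appendix 2 with its use during treatment.
- Do not instead keep the EEN-only review and restrict outcome 10 to events elicited at visits 3 and 4. As shown above, that could reverse the bias.

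The cost is about 33 short calls (100 patients over three arms), one diary line and slightly more contact in the CS arm. No dose or clinical rule changes. If a week-3 contact for CS is already intended, the contact itself needs only one sentence in Study design, and the common enquiry still has to be specified.
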